### B&A Program

At the Baseline visit, subjects will be randomly assigned to one of the three treatment groups (up to 50 per group) using an encoded B&A program supplied by the Sponsor. The subjects will be stratified based on DMI Severity Score and age. Subjects residing in the same household will be assigned to the same treatment group.

## 11. Determination of Sample Size

Forty-five subjects per treatment group completing the study will ensure 80% power to detect a difference of at least 0.66 units on the 5-points PPAQ 1 scale in the Positive Control or Experimental rinse relative to water with a standard deviation of 1.1, in one-sided testing at a 2.5% significance level (based on published research). A target of up to 50 subjects will be recruited per group (total of up to 150) allowing for a 10% dropout rate.

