## 14. Hypotheses

The following hypotheses will be tested using a serial gatekeeping approach as specified below (Multiple Testing Problems in Pharmaceutical Statistics, Chapter 5: Gatekeeping Procedures in Clinical Trials, editors A Dmitrienko, AC Tamhane, F Bretz, Chapman and Hall 2010.)

The primary endpoint will be the response to "relieving the discomfort of dry mouth" from the modified PPAQ I.

For model sensitivity Hypothesis 1 will be tested at Hour 4 at Day 1:

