### **Hypothesis 1**

**Null:** The mean response for the Positive Control Rinse is less than or equal to the mean response for the Water Control.

**Alternative:** The mean response for the Positive Control Rinse is greater than the mean response for the Water Control.

If the Null Hypothesis is rejected for Hypothesis 1 then Hypotheses 2 will be tested for Hour 4 at Day 1:

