### **Hypothesis 2**

**Null:** The mean response for the Experimental Rinse is less than or equal to the mean response for the Water Control.

**Alternative:** The mean response for the Experimental Rinse is greater than the mean response for the Water Control.

If the Null Hypothesis is rejected for Hypothesis 2 then Hypotheses 3 will be tested for Hour 6 at Day 1:

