## 15. Statistical and Analytical Plans

### Analysis Population

Efficacy analysis will be conducted on the Intent-to-treat (ITT) population, defined as those subjects who received study treatment and have at least one post-treatment efficacy measurement. This will be the primary population for the efficacy analysis.

Subjects who require “rescue product” will complete the questionnaire at the time of rescue. These responses will then be carried forward to all subsequent timepoints for that day for purposes of statistical analyses. No imputation for other missing data will be performed unless more than 10% of data are missing. If more than 10% of data are missing, the last observation will be carried forward for that day for purposes of statistical analyses.

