### Efficacy Analyses

Summary statistics (e.g., means, standard deviations, frequencies, etc.) of the demographic characteristics and questionnaire responses will be calculated for each treatment group and applicable time points.

For the primary comparisons, the treatment groups will be compared using the analysis of covariance method with the response to “relieving the discomfort of dry mouth” from the modified PPAQ I as the response and DMI severity score, response to “how moist does your mouth feel right now” at baseline, or response to “how dry does your mouth feel right now” at baseline may be used as the covariates. Statistical comparisons will be one-sided with a significance level of 0.025.

$$Y_{i1} = \mu + \alpha \cdot Covariate_i + \beta \cdot Group_i + \epsilon_i$$

The secondary endpoints of interest will be the responses to “how moist does your mouth feel right now” and “how dry does your mouth feel right now” from the MD questionnaire immediately after use at Day 1. The Experimental rinse group will be compared to water using the analysis of covariance method with the immediate score as the response and DMI severity score and baseline response may be used as the covariates.

Responses to all other questions and time points will be of tertiary interest. Additional analyses of the data may be performed.

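### Section 11's 80% power is for one rinse-versus-water test on its own; after the Section 14 gate, power for the Experimental rinse claim at Hour 4 is about 70% on the same assumptions

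*Combined protocol and SAP*

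**What the plan says.** Section 11 (Determination of Sample Size) says: "Forty-five subjects per treatment group completing the study will ensure 80% power to detect a difference of at least 0.66 units" on the five-point PPAQ I scale, "in the Positive Control or Experimental rinse relative to water with a standard deviation of 1.1", one-sided at 2.5%. It then adds a recruitment margin: "A target of up to 50 subjects will be recruited per group (total of up to 150) allowing for a 10% dropout rate". It names no time point and does not mention any order of testing.

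Section 14 (Hypotheses) sets a serial gatekeeping sequence on the PPAQ I dry-mouth relief item:

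- Hypothesis 1, Positive Control against water: "For model sensitivity Hypothesis 1 will be tested at Hour 4 at Day 1".
- Hypothesis 2, Experimental rinse against water: "If the Null Hypothesis is rejected for Hypothesis 1 then Hypotheses 2 will be tested for Hour 4 at Day 1".
- Hypothesis 3, Experimental rinse against water at a later hour: "If the Null Hypothesis is rejected for Hypothesis 2 then Hypotheses 3 will be tested for Hour 6 at Day 1".

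Section 15 (Efficacy Analyses) uses the same error rate for every test: "Statistical comparisons will be one-sided with a significance level of 0.025". The analysis is by ANCOVA, but the covariates are listed only as ones that may be used. The analysis population is "those subjects who received study treatment and have at least one post-treatment efficacy measurement".

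**The concern.** Section 11 promises 80% power for the Positive Control or the Experimental rinse as if each were tested on its own. Section 14 does not provide a stand-alone test of the Experimental rinse. A real Experimental effect can go unclaimed at Hour 4 in two ways: its own test fails, or the Positive Control's test fails and Hypothesis 2 is never reached. Section 11 counts only the first.

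The Experimental rinse is one of the two products compared with water in the objective (Section 2), and the only one in Hypotheses 2 and 3. A reader of Section 11 would take the risk of missing a true 0.66 difference for it to be 20%. Under the plan's own rules that risk is higher. It also depends on the Positive Control's true effect, which Section 11 does not discuss as an input to the Experimental claim.

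**Working it through.** **Inputs.** From Section 11: n = 45 completers per group (50 recruited), difference 0.66, SD 1.1, one-sided 0.025. From Section 14: Hypothesis 2 can be claimed only if Hypotheses 1 and 2 are both rejected, and both use the water arm. Taking 0.66 for both rinses at Hour 4 is the natural reading of Section 11. No variance reduction from covariates is assumed.

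**1. The plan's own figure.** The noncentrality of one comparison is 0.66 / (1.1 × √(2/45)) = 2.846. With 88 degrees of freedom, the noncentral t gives power 0.804 at n = 45 and 0.795 at n = 44. So 45 is the smallest group size that gives 80% for a single test. The recruitment target also reproduces: 45 / (1 − 0.10) = 50. At n = 50 the noncentrality is 3.000 and single-test power is 0.844.

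**2. Correlation of the two tests.** With equal group sizes and SDs, each mean difference has variance 2σ²/n. The two differences share the water mean, so their covariance is σ²/n and their correlation is 0.5. Multiplying the two powers as if independent (0.812 × 0.812 = 0.660 on the normal approximation) would therefore be too low.

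**3. Power for Hypothesis 2 after the gate.** The quantity needed is P(T1 > c and T2 > c), with both noncentralities equal and correlation 0.5. On the normal approximation, for example, this is P(Z1 > 1.960 − 2.846 and Z2 > 1.960 − 2.846).

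| Method | n = 45 | n = 50 |
|---|---|---|
| Bivariate normal | 0.704 | 0.759 |
| t tests, error pooled over three groups | 0.697 | 0.753 |
| Separate two-group t tests (simulated) | 0.692 | 0.749 |
| Single ungated test, for comparison | 0.804 | 0.844 |

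**4. Dependence on the Positive Control.** The Experimental effect is held at 0.66 and the pooled error is used. The Positive Control effects other than 0.66 are assumptions, chosen to show the range.

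| True Positive Control effect | Power for Hypothesis 1, n = 45 | Gated power for Hypothesis 2, n = 45 | Gated power for Hypothesis 2, n = 50 |
|---|---|---|---|
| 0.40 | 0.402 | 0.375 | 0.416 |
| 0.50 | 0.572 | 0.519 | 0.572 |
| 0.66 | 0.807 | 0.697 | 0.753 |
| 0.80 | 0.929 | 0.774 | 0.822 |
| 1.00 | 0.990 | 0.804 | 0.845 |

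At n = 45 the gate costs almost nothing only when the Positive Control effect is near 1.0.

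**5. Scale.** With 0.66 for both rinses and the pooled error, gated power for Hypothesis 2 is 0.791 at 54 evaluable per group, 0.800 at 55 and 0.809 at 56.

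**6. Hypothesis 3.** This lies one gate further on, so its power is lower still. If 0.66 and SD 1.1 also hold at Hour 6, power at n = 45 is 0.606, 0.627 or 0.658 for an Hour 4–Hour 6 correlation of 0.5, 0.7 or 0.9. None of these inputs is in the documents.

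**The case against.** The strongest reply is that Section 11 contains no miscalculation. It uses pairwise wording, with an *or* between the two rinses, and never claims 80% for the sequence. Quoting pairwise power beside a fixed sequence is common. This is right about the arithmetic, but the wording promises the figure without qualification, and for the Experimental rinse it describes a test that Section 14 does not offer.

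Second, 45 may be too low an n for this endpoint. Hypothesis 2 is assessed on Day 1, whereas 45 counts subjects who finish the study at Day 8. The analysis population needs only one measurement after treatment, and rescue responses are carried forward within the day. The number evaluable at Hour 4 may well be nearer 50. This stands in part: about 75% is then the better figure. But 50 is a ceiling on recruitment, 45 is the plan's own planning number, and 75% is still short of 80%.

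Third, ANCOVA could reduce the residual variance. Reaching 80% after the gate needs the equivalent of about 55 per group, so the covariates would have to explain about 1 − 45/55 = 18% of the variance at n = 45, or 1 − 50/55 = 9% at n = 50. That is possible. However, the covariates are optional, the plan states no correlation, and 1.1 may already be a residual SD.

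Fourth, the true effects may exceed 0.66, since Section 11 says *at least*. But the 80% is itself the figure at 0.66, so the fair comparison is at the same value. Finally, once Hypothesis 1 has passed, power for Hypothesis 2 is about 0.697 / 0.807 = 86% at n = 45. That is true, but it is conditional on the outcome of the gate and is not the power at the planning stage.

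**Conclusion.** The concern holds. The 80% is correct for Hypothesis 1 and for either rinse-versus-water comparison taken alone. It is not the power to claim Hypothesis 2 under Section 14. On the plan's own inputs, with a true difference of 0.66 for both rinses, that power is about 70% at 45 per group and about 75% if 50 per group are evaluable. The risk of missing a real Experimental effect at Hour 4 is thus about 25–30%, against the 20% implied.

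The result assumes equal groups, a common SD of 1.1 and no gain from covariates. Any such gain, or a Positive Control effect above 0.66, would raise the figure; a weaker Positive Control would lower it. The gate and its control of type I error are not in question. The secondary comparisons of moistness and dryness immediately after use on Day 1 are not stated to belong to the chain, so these figures do not apply to them. The point should be fixed, but it concerns the power statement and not the design.

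**What to change.** Restate Section 11, for example:

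> With 45 completers per group, power is 80% for Hypothesis 1 and for each rinse-versus-water comparison taken alone (difference 0.66, SD 1.1, one-sided 0.025). Because Hypothesis 2 is tested only if Hypothesis 1 is rejected, power to claim Hypothesis 2 is about 70% if the true difference is 0.66 for both rinses (about 75% if 50 per group are evaluable at Hour 4). Power for Hypothesis 2 depends on the true effect of the Positive Control.

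If the sponsor expects a larger Positive Control effect or a gain from covariates, Section 11 should state the assumed value and recompute. Power for Hypothesis 3 need not be given. If it is, it should be shown as lower than that for Hypothesis 2, with its Hour 6 effect, SD and between-hour correlation labelled as assumptions.

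The cost is two or three sentences and a less favourable stated power for the Experimental claim. Sample size, order of testing and type I error are unchanged.

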## 12. Efficacy Variables

### DMI Questionnaire

The following set of questions will be asked at the Acclimation (Visit 1).

(Severity Score = sum of 4 questions where: strongly disagree= -2, disagree= -1, disagree a little=0, agree a little=1, agree=2, strongly agree=3). Subjects to answer 2 or more of the 4 questions below positively in order to continue into the study. For summing the DMI score for randomization purposes, negative scores (strongly disagree= -2, disagree= -1) will be calculated as 0 in the database.

How much do you agree or disagree that you experience the following? (strongly disagree, disagree, disagree a little, agree a little, agree, strongly agree)

- 1) No moisture in the mouth
- 2) Lips sticking to teeth
- 3) Tongue sticking to roof of mouth
- 4) Throat feels dry

### Baseline MD Questionnaire

The following set of questions will be asked at Baseline/Day1 (Visit 2).

Subjects to answer:

- 1) How moist does your mouth feel now? (0=not at all to 10=very moist)
- 2) How dry does your mouth feel now? (0=very dry to 10=not dry at all)

Immediate MD Questionnaire

The following set of questions will be asked at Baseline/Day1 (Visit 2).

Subjects to answer:

- 1) How moist does your mouth feel now? (0=not at all to 10=very moist)
- 2) How dry does your mouth feel now? (0=very dry to 10=not dry at all)

PPAQ I/ MD Questionnaire

The following set of questions will be asked at Baseline/Day1 (Visit 2) – 30 minutes, 1-hour, 2-hour, 4-hour, 6-hour.

Since you have been using the product, please rate each of the following at this timepoint: (Select one response for each attribute)- excellent=5, very good=4, good=3, fair=2, poor=1:

- 1) Relieves the discomfort of your dry mouth
- 2) Feels comfortable in your mouth
- 3) Soothes your mouth
- 4) Allows you to speak without difficulty
- 5) Effectively moistens your mouth
- 6) Effectively lubricates your mouth
- 7) Helps to freshen your breath
- 8) Protects your mouth from drying out
- 9) Provides whole mouth comfort
- 10) Helps you to swallow without difficulty
- 11) Helps your mouth feel "normal"

Subjects to answer:

- 1) How moist does your mouth feel now? (0=not at all to 10=very moist)
- 2) How dry does your mouth feel now? (0=very dry to 10=not dry at all)

PPAQ II Questionnaire

The following set of questions will be answered at home before Day 8 (Visit 3).

Since you have been using the product over the last 8 days, please rate each of the following as they apply to the rinse study product: (Select one response for each attribute)- excellent=5, very good=4, good=3, fair=2, poor=1:

- 1) Provides relief all night
- 2) Reduces the number of times you wake up from dry mouth
- 3) Feeling less parched when you wake up
- 4) Having a long-lasting dry mouth relief
- 5) Having a long-lasting lubricating effect
- 6) Having a long-lasting moisturizing effect

PPAQ I Questionnaire

The following set of questions will be asked at Day8 (Visit 3)- 30 minutes, 1-hour, 2-hour, 4-hour, 6-hour.

Since you have been using the product, please rate each of the following at this timepoint: (Select one response for each attribute)- excellent=5, very good=4, good=3, fair=2, poor=1:

- 1) Relieves the discomfort of your dry mouth
- 2) Feels comfortable in your mouth
- 3) Soothes your mouth
- 4) Allows you to speak without difficulty
- 5) Effectively moistens your mouth
- 6) Effectively lubricates your mouth
- 7) Helps to freshen your breath
- 8) Protects your mouth from drying out

- 9) Provides whole mouth comfort
- 10) Helps you to swallow without difficulty
- 11) Helps your mouth feel "normal"

## 13. Safety Variables

### Oral Examination

Assessment of the oral soft tissue is conducted via a visual examination of the oral cavity and perioral area utilizing a standard dental light, dental mirror, and gauze. The structures examined include the gingiva (free and attached), hard and soft palate, oropharynx/uvula, buccal mucosa, tongue, floor of the mouth, labial mucosa, mucobuccal/mucolabial folds, lips, and perioral area. Assessment of the oral hard tissues are conducted via a visual examination of the dentition and restorations utilizing a standard dental light, dental mirror, and air syringe. All abnormal findings are recorded and categorized by their location with hard tissue findings categorized as "other-oral." An AE is recorded if a new abnormal finding is noted after treatment application or any abnormal finding noted prior to treatment application increases in severity after treatment is applied.

## 14. Hypotheses

The following hypotheses will be tested using a serial gatekeeping approach as specified below (Multiple Testing Problems in Pharmaceutical Statistics, Chapter 5: Gatekeeping Procedures in Clinical Trials, editors A Dmitrienko, AC Tamhane, F Bretz, Chapman and Hall 2010.)

The primary endpoint will be the response to "relieving the discomfort of dry mouth" from the modified PPAQ I.

For model sensitivity Hypothesis 1 will be tested at Hour 4 at Day 1:

### **Hypothesis 1**

**Null:** The mean response for the Positive Control Rinse is less than or equal to the mean response for the Water Control.

**Alternative:** The mean response for the Positive Control Rinse is greater than the mean response for the Water Control.

If the Null Hypothesis is rejected for Hypothesis 1 then Hypotheses 2 will be tested for Hour 4 at Day 1:

### **Hypothesis 2**

**Null:** The mean response for the Experimental Rinse is less than or equal to the mean response for the Water Control.

**Alternative:** The mean response for the Experimental Rinse is greater than the mean response for the Water Control.

If the Null Hypothesis is rejected for Hypothesis 2 then Hypotheses 3 will be tested for Hour 6 at Day 1:

### **Hypothesis 3**

**Null:** The mean response for the Experimental Rinse is less than or equal to the mean response for the Water Control.

**Alternative:** The mean response for the Experimental Rinse is greater than the mean response for the Water Control.

## 15. Statistical and Analytical Plans

### Analysis Population

Efficacy analysis will be conducted on the Intent-to-treat (ITT) population, defined as those subjects who received study treatment and have at least one post-treatment efficacy measurement. This will be the primary population for the efficacy analysis.

Subjects who require “rescue product” will complete the questionnaire at the time of rescue. These responses will then be carried forward to all subsequent timepoints for that day for purposes of statistical analyses. No imputation for other missing data will be performed unless more than 10% of data are missing. If more than 10% of data are missing, the last observation will be carried forward for that day for purposes of statistical analyses.

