#### Baseline/Day 1 (Visit 2)

Continuance criteria will be assessed. Subjects will have an Oral Examination at the site. Subjects will be randomly assigned to one of three treatment groups by a Balance & Assignment (B&A) program based on age and DMI severity score. Assigned treatment product kit boxes will be distributed and written instructions reviewed. In addition, all groups will be instructed to continue using the acclimation products per acclimation instructions. Subjects will be sent home with copies of questionnaires, their assigned kit box, the product diary, and the standardized snack. While at home, subjects will complete the Baseline MD questionnaire over the phone with site staff. Subjects will then use their assigned product for the first time and then a timer will be set for 6 hours. Immediately following the product use, subjects will complete the Immediate MD Questionnaire over the phone with site staff. Site staff will contact the subjects at home at the corresponding timepoints for completing the remaining questionnaires, (the PPAQ I/ MD 30-minute Questionnaire, the PPAQ I/ MD 1-hour, 2-hour, 4-hour and 6-hour Questionnaires).

Subjects will be instructed to refrain from eating, drinking, smoking, using their test products, using tobacco, using a medicated lozenge, chewing gum, or breath mints during the 6-hour test period. Subjects may consume their provided standardized snack immediately after the 4-hour questionnaire.

Should a subject not be able to follow the drinking or eating restrictions for the full six hours (i.e. require a rescue product such as water), the subject will be asked to fill out the next set of questionnaires, and then they will be allowed to resume normal activity for the rest of Day 1. Site staff will record the time the subject completed the questionnaires in General Comments. If desired, the subject will be allowed to remain in the study.

After the 6-hour questionnaire, subjects will be reminded to adhere to their assigned product use instruction sheet for the duration of the study. Subjects will be asked to complete the product diary tracking their product usage and water intake. Subjects from all groups will be allowed to sip water as needed on Days 2 – 7. Subjects will be reminded to bring their acclimation and treatment kit boxes and completed product diary to their next study visit.

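### The primary missing-data method switches to LOCF above an undefined 10% missing, and LOCF presumes the persistence of relief that the Hour 4 and Hour 6 tests are meant to show

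*Combined protocol and SAP*

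**What the plan says.** Section 15 (Analysis Population) sets two branches for missing ratings other than those after rescue. Below the threshold: "No imputation for other missing data will be performed unless more than 10% of data are missing". Above it: "If more than 10% of data are missing, the last observation will be carried forward for that day for purposes of statistical analyses". Nothing says whether the 10% is counted over subjects, items, timepoints or days, pooled or by arm, or with carried rescue values included. A separate rule, which applies at any level of missingness, carries the rating given at rescue forward through that day. The ITT set needs only one post-treatment measurement, so it can include subjects with no Hour 4 or Hour 6 rating.

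Section 14 tests the dry-mouth discomfort item on Day 1. Hypotheses 1 and 2 compare the positive control and the experimental rinse with water at Hour 4. Then: "If the Null Hypothesis is rejected for Hypothesis 2 then Hypotheses 3 will be tested for Hour 6 at Day 1". Under Efficacy Analyses, "the treatment groups will be compared using the analysis of covariance method", and "Statistical comparisons will be one-sided with a significance level of 0.025". No missing-data sensitivity analysis is specified; the section says only that further analyses are possible.

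Section 3 (Baseline/Day 1) adds: "Subjects may consume their provided standardized snack immediately after the 4-hour questionnaire".

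**The concern.** There are two problems.

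First, the primary analysis is settled only once the amount of missing data is known. Because the denominator is undefined, two analysts could apply the rule to the same data and run different primary analyses. The switch also changes who is analysed: an ITT subject without an Hour 4 rating is left out on one side of the threshold and counted on the other.

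Second, LOCF suits these tests poorly. They concern late relief, and LOCF replaces a missing late rating with an earlier one. If an early benefit has faded by the tested hour, LOCF brings the early difference into the test and can support a false duration claim. If ratings fall in all arms and water has more missing ratings, LOCF works against the rinse. For Hypothesis 3, every carried value was given at or before Hour 4, so before any snack, yet it is analysed as an Hour 6 rating.

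The rating taken at rescue is a fresh rating under its own rule and is not part of this bias claim.

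**Working it through.** **1. The plan's own figure.** Section 11 gives a difference of 0.66, SD 1.1, one-sided 0.025 and 80% power.

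n = 2 × (1.960 + 0.842)² × (1.1/0.66)² = 43.6, so 44 per group by the normal approximation. The t-test needs 45 (power 80.4%; 79.5% at 44). Then 45/(1 − 0.10) = 50. The stated sample size reproduces and is not affected by this point.

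**2. The denominator.** Assume 0, 4, 8, 12 and 16% missing at 0.5, 1, 2, 4 and 6 hours. Over all Day 1 ratings this is (0 + 4 + 8 + 12 + 16)/5 = 8%, so no imputation. At Hour 4 it is 12% and at Hour 6 it is 16%, so LOCF. The text allows either reading.

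**3. Chance of crossing the threshold** (exact binomial). At a true missing rate of 10%, the observed rate exceeds 10% with probability 43% over 150 subjects, 42% over 100 and 38% in one arm of 50. Over 150 subjects the probability is 0.4% at a true rate of 5% and 73% at 12%.

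**4. LOCF bias.** With missingness unrelated to the ratings,

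bias = m_E × d_E − m_W × d_W,

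where m is the share missing at the tested hour, d is the mean fall from the last rating to that hour, E is the experimental rinse and W is water. With n = 45, SE = 1.1 × √(2/45) = 0.232, and the one-sided error is about 1 − Φ(1.960 − bias/SE).

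- *Case (a), Hypothesis 2.* Rinse effect 0.66, 0.50, 0.25 and 0 at 0.5, 1, 2 and 4 h. Equal dropout by arm, spread evenly over 1, 2 and 4 h. Bias = (m/3) × (0.66 + 0.50 + 0.25) = (m/3) × 1.41.
- *Case (b), Hypothesis 3.* Effect 0.66 through Hour 4 and 0 at Hour 6, dropout spread over 1, 2, 4 and 6 h. Bias = m × 0.66.

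The simulations used 10,000 three-arm trials per scenario, 45 per arm, AR(1) correlation 0.7, monotone missingness after the 30-minute rating and no baseline covariate. Monte Carlo SE is about 0.2 percentage points.

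| Case | Missing at tested hour | Bias | Error, closed form (ungated) | Error, LOCF simulated | Error, repeated measures |
|---|---|---|---|---|---|
| (a) H2 | 12% | 0.056 | 4.3% | 4.6% | 2.3–2.5% |
| (a) H2 | 17% | 0.080 | 5.3% | 5.0% | 2.3–2.5% |
| (a) H2 | 27% | 0.127 | 7.9% | 7.8% | 2.3–2.5% |
| (b) H3 | 12% | 0.079 | 5.3% | 5.0% (gated) | 2.5% (gated) |
| (b) H3 | 17% | 0.112 | 7.0% | 6.9% (gated) | 2.4% (gated) |
| (b) H3 | 27% | 0.178 | 11.7% | 10.6% (gated) | 2.0% (gated) |

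In (a), available-case analysis gives 2.4–2.5%. If the positive control truly has +0.66, gating on Hypothesis 1 changes the LOCF errors only to 4.5%, 5.0% and 7.6%.

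**5. No bias, and bias the other way.** With equal profiles and equal missingness, LOCF error is 2.1–2.7%. With scores falling from 3.2 to 2.7 by Hour 4 and no true difference, ungated error is 1.5% when 27% are missing on water and 12% on the rinse, and 4.2% when reversed. A sharper example has 50 per arm, correlation 0.6 and a fall of 1.0 in both arms. With 20% missing on the rinse and 5% on water, bias = 0.20 − 0.05 = +0.15 and error is 9.4%. Reversed, bias is −0.15 and error is 0.4%. With a true difference of 0.66, LOCF power is then 94% or 59%, against about 79% for observed cases.

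**6. Missingness driven by a low previous rating (d).** The treatment effect is as in (b), and the log-odds of dropout fall by 1 per rating point.

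| Missing at Hour 6, water vs rinse | Method | H3 bias | H3 error |
|---|---|---|---|
| 17% vs 9% | LOCF | +0.08 | 4.8% |
| 17% vs 9% | Available-case | −0.04 | 1.7% |
| 17% vs 9% | Repeated measures | 0.00 | 2.1% |
| 26% vs 16% | LOCF | +0.12 | 7.3% |
| 26% vs 16% | Available-case | −0.06 | 1.6% |
| 26% vs 16% | Repeated measures | 0.00 | 2.3% |

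**The case against.** The strongest objection is that the LOCF branch may never be used. The tested ratings fall within six hours of first use. Staff telephone each subject and enter the answers directly, and rescued subjects are covered by a separate rule. The 10% dropout in section 11 concerns study completion, not Day 1 calls. At a true 5% missing rate, the chance of crossing 10% is 0.4% over 150 subjects and 3.8% in one arm of 50. This stands: the error rates above apply only if LOCF is triggered.

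The rule is also prespecified and depends on how much is missing, not on the ratings or the treatment effect. That is correct, but the open denominator still leaves a choice to be made after the data are seen.

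The scenarios are unfavourable ones. Case (b) needs a full effect at Hour 4 and none at Hour 6. If calls are missed independently rather than by dropout, errors in (a) fall to about 3.5%, 4.3% and 5.1%; case (b) is not reduced. The snack is optional, standardised and open to all arms, and no differential effect of it has been shown. These points temper the size but do not remove the defect.

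Finally, available-case ANCOVA at every level of missingness would also remove the switch, and in (d) its error is conservative. It is a defensible minimum. The repeated-measures simulations contained no rescued subjects and no baseline covariate, so the absence of bias is shown for a simpler model than the one proposed below.

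**Conclusion.** The concern holds and should be fixed. The text shows that the method is conditional, that the threshold is undefined, and that LOCF substitutes earlier ratings at the tested hours. No other section corrects this.

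The size is conditional. It rests on assumed missingness of 12–27% and on assumed effect profiles, neither of which the documents give. Under those assumptions, one-sided error rises from 2.5% to 4.6–7.8% for Hypothesis 2, and to 5.0–10.6% for Hypothesis 3 after both gates. Gatekeeping gives Hypothesis 3 little protection when the rinse truly works at Hour 4 but not at Hour 6. Other patterns make the test conservative and cost power, and equal profiles with equal missingness leave it unaffected. Confidence is high in the defect, and lower in any single error rate.

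**What to change.** Before unblinding, delete the 10% switch and remove LOCF from the primary analysis. State that non-rescue missing ratings are not imputed at any level of missingness.

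- **Primary model:** one likelihood-based repeated-measures model (REML) for the primary item on the five Day 1 PPAQ I timepoints. Include treatment, time, treatment-by-time and baseline covariates fixed in advance, with unstructured covariance and a named fallback if it does not converge.
- **Contrasts:** Hypotheses 1 and 2 are the Hour 4 contrasts, and Hypothesis 3 is the Hour 6 contrast.
- **Sensitivity:** report LOCF here only.
- **Rescued subjects:** keep the planned carry-forward of the rating taken at rescue in the analysis, and state the estimand it represents (relief up to rescue stands for later timepoints). Add a sensitivity analysis in the same model that treats post-rescue timepoints as missing.

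If ANCOVA is preferred, use available cases at every level of missingness and accept the bias of −0.04 to −0.06 seen in (d).

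The cost is SAP wording and slightly more programming; no new data are needed. If a 0.66 effect persists and 17% of 45 per arm are missing at Hour 4, Hypothesis 2 power is 74.3% with repeated measures and 72.8% with available cases. LOCF shows 80.6%, but only because it counts carried values as observed. Starting from the 50 recruited per arm, available-case power is about 77%. In the 26% vs 16% case of (d), Hypothesis 2 power is 74.8% with repeated measures and 68.8% with available cases.
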